* Indicates Associate Investigators who will not be involved in clinical decisions or ¹⁸F-DCFBC ordering.

Study Sponsor: National Cancer Institute, Cancer Imaging Program

IND #: 122053

NCI-Supplied Agent(s): ¹⁸F-DCFBC

Other Agent(s): ¹⁸F NaF

Manufacturer: Leidos Biomedical Research, Inc.

CC Protocol Number: 14-C-0140
Abbreviated Title: DCFBC in prostate cancer
Version date: 10/27/2015
CIP #: 9622

Précis

Background

- Prostate cancer is the second leading cause of cancer deaths in American men
- Current methods of imaging advanced prostate cancer (CT and bone scan) are non-specific and new, more specific molecular imaging probes are sought.
- Many prostate cancers express the prostate specific membrane antigen (PSMA) a transmembrane protein with NAALADase enzymatic activity. PSMA is also expressed in angiogenesis but otherwise has limited expression in normal tissue.
- ¹⁸F-DCFBC is a radiolabeled PET agent which binds with high affinity to PSMA and through whole-body non-invasive functional imaging, may provide new information on the expression of PSMA.

Primary Objective

- To assess the ability of ¹⁸F-DCFBC to differentiate between tumorous and non-tumorous tissues in localized, recurrent (based on rising PSA post treatment) and metastatic prostate cancer

Eligibility

- Subject is ≥ 18 years old
- ECOG 0-2 with adenocarcinoma of the prostate and fits criteria for one of the following:
 - ARM 1
 - Patients with known localized prostate cancer with a soft tissue lesion at least 6mm or greater.
 - A multiparametric MRI (standard of care at the NIH Clinical Center) must be performed within 4 months of ¹⁸F-DCFBC injection with findings suggestive for prostate cancer and confirmed with histopathology.
 - ARM 2
 - Patients with biochemical prostate cancer relapse after definitive treatment
 - For patients status post radiation therapy for prostate cancer, any PSA increase from post radiation therapy nadir
 - OR
 - For patients status post prostatectomy, a PSA ≥ 0.2 ng/ml
 - Nonspecific or no evidence for disease on standard imaging modality
 - ARM 3
 - Patients with identifiable metastatic disease on a conventional imaging modality. If only soft tissue metastasis, one lesion must measure 6mm or greater. Patients must have confirmation of prostate cancer prior to ¹⁸F-DCFBC imaging.

[figure not shown]
Design

CC Protocol Number: 14-C-0140
Abbreviated Title: DCFBC in prostate cancer
Version date: 10/27/2015
CIP #: 9622

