1.2 Secondary Objectives

- Compare the distribution ^{18}F -DCFBC with multiparametric MRI and whole mount histopathology in patients undergoing prostatectomy
- Evaluate the distribution ^{18}F -DCFBC uptake in prostate cancer patients with biochemical relapse (site of recurrence unknown)
- Compare focal ^{18}F -DCFBC uptake with focal abnormalities identified on standard of care imaging
- Compare the uptake of ^{18}F -DCFBC in bone with respect to Na^{18}F PET/CT in patients with metastatic disease (the emerging gold standard, for detection of bony metastases).
- Evaluate the change over time in ^{18}F -DCFBC distribution in patients with known metastatic disease with clinical follow-up data 4-6 months post baseline ^{18}F -DCFBC PET/CT (e.g. understand the effect of androgen deprivation therapy (ADT) on ^{18}F -DCFBC uptake)

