3 PATIENT SELECTION

3.1 Eligibility Criteria

- 3.1.1 Subject is ≥ 18 years old
- 3.1.2 Platelet count $> 50,000/\text{mm}^3$
- 3.1.3 Eastern Cooperative Oncology Group (ECOG) Performance score of 0 to 2.
- 3.1.4 Ability to provide informed consent. All subjects must sign an informed consent form indicating their understanding of the investigational nature and risks of the study before any protocol-related studies are performed.
- 3.1.5 Categories
 - 3.1.5.1 ARM 1 only
 - 3.1.5.1.1 For patients with presumed localized disease (any T, N0, M0), a multiparametric MRI (standard of care at the NIH Clinical Center) must be performed within 4 months of the ^{18}F -DCFBC injection with findings suggestive for prostate cancer and a prostate lesion at least 6mm or greater. Must have histopathologic confirmation of prostate cancer prior to ^{18}F -DCFBC imaging.
 - 3.1.5.2 ARM 2 only:
 - 3.1.5.2.1 For patients status post radiation therapy for prostate cancer, any PSA increase from post radiation therapy nadir

OR

- 3.1.5.2.2 For patients status post prostatectomy, a PSA ≥ 0.2 ng/ml
- 3.1.5.2.3 Nonspecific or no evidence for disease on standard imaging modality
- 3.1.5.3 ARM 3 only:
 - 3.1.5.3.1 Patients must have identifiable metastatic disease on at least 1 clinically indicated imaging modality. If only soft tissue metastasis, one lesion must measure at least 6mm or greater. Patients must have confirmation of prostate cancer prior to ^{18}F -DCFBC imaging.

Note: A patient who is eligible for one arm, subsequently may cross-over into a different arm.

CC Protocol Number: 14-C-0140
Abbreviated Title: DCFBC in prostate cancer
Version date: 10/27/2015
CIP #: 9622

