4 STUDY IMPLEMENTATION

4.1 Study Design

This is an open-label, 3-armed single-center pilot study. 110 evaluable subjects will be enrolled into the study (12 evaluable patients in arm 1; 78 evaluable patients in arm 2, and 20 evaluable patients in arm 3). An evaluable patient is defined as a patient who completes all required study procedures according to the assigned study arm. In order to allow for a small number of nonevaluable patients, the accrual ceiling will be set at 125.

Informed consent will be obtained prior to study enrollment. All subjects will undergo ^{18}F DCFBC injection and PET/CT imaging.

Patients in Arms 1 and 2 will undergo a single ^{18}F DCFBC PET/CT.

Patients in Arm 1 will have undergone a standard of care biopsy or clinically indicated prostatectomy. Specimens will be whole mounted on glass slides and regions of malignant tumor will be marked by the pathologist.

When possible, uptake of ^{18}F DCFBC depicted on PET/CT in Arms 2 and 3 will be validated with biopsy.

Patients in Arm 2 will be followed for clinical, imaging or pathologic data that may be obtained by their medical team within 12 months of imaging to determine if associations with ^{18}F DCFBC PET/CT can be seen.

CC Protocol Number: 14-C-0140
Abbreviated Title: DCFBC in prostate cancer
Version date: 10/27/2015
CIP #: 9622

Subjects in the metastatic disease arm (Arm 3) (as well as individuals who cross over into Arm 3) will undergo 2 separate ^{18}F DCFBC PET/CT imaging sessions, one at initial enrollment, and a second upon clinical follow-up (4-6 months after baseline ^{18}F DCFBC).

Patients in Arm 3 will also undergo a whole body Na^{18}F PET/CT scan within 3 weeks of each ^{18}F DCFBC to assess for potential early bone metastases. Changes in distribution of each radiotracer over the 4-6 month period will be compared with clinical data and imaging (obtained as standard of care) at that time. Each ^{18}F DCFBC PET/CT will be compared with the corresponding Na^{18}F PET/CT scan when obtained.

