4.2 Stratification Procedures

4.2.1 Categories

- ARM 1
 - For patients in the localized disease arm, a multiparametric MRI (standard of care at the NIH Clinical Center) with findings suggestive for prostate cancer must be performed in the NCI Molecular Imaging Clinic (MIC) within 4 months of enrollment and histopathologic confirmation of prostate cancer must be done
- ARM 2
 - Patients enrolling into the biochemical relapse arm:
 - For patients status post radiation therapy, any PSA increase from post radiation therapy nadir
 - OR**
 - For patients status post prostatectomy, a PSA ≥ 0.2 ng/ml
 - Nonspecific or no evidence for disease on standard imaging modality
- ARM 3
 - Patients in the metastatic monitoring arm must have identifiable metastatic disease on at least 1 imaging modality.

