14.2 Secondary Analysis

For patients with localized disease, the diagnostic accuracy of ^{18}F -DCFBC PET/CT will be compared with multiparametric MRI using the sector-based analysis. Patient-specific sensitivity and specificity will be estimated and differences in sensitivity and specificity between different modalities will be tested by the Wilcoxon signed-rank test. Change of ^{18}F -DCFBC uptake for patients with metastatic disease over time will be estimated by the linear mixed effect model where random intercept will be used to account for the intra-patient correlation of longitudinal ^{18}F -DCFBC uptake. In addition, in patients with metastatic prostate cancer to bone, the uptake of ^{18}F -DCFBC will be correlated with the uptake of the emerging gold standard, ^{18}F Sodium Fluoride PET/CT by the Spearman rank correlation.

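### Arm 1 admits only men with a suggestive MRI, so the planned DCFBC-versus-MRI sensitivity comparison is tilted towards MRI by an amount the documents cannot fix

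*Combined protocol and SAP*

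**What the plan says.** Entry to Arm 1 depends on MRI. Section 3.1.5.1.1 asks for a multiparametric MRI "with findings suggestive for prostate cancer and a prostate lesion at least 6mm or greater", and adds in a separate sentence: "Must have histopathologic confirmation of prostate cancer prior to" DCFBC imaging. The précis has the same rule in a tighter form, with MRI done within 4 months of the "injection with findings suggestive for prostate cancer and confirmed with histopathology". Section 4.2.1 repeats it: an MRI "with findings suggestive for prostate cancer must be performed in the NCI Molecular Imaging Clinic (MIC) within 4 months of enrollment". None of the three places sets a condition on the DCFBC result.

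The comparison is a named secondary objective. Section 1.2 sets the DCFBC distribution against the other sources "with multiparametric MRI and whole mount histopathology in patients undergoing prostatectomy". Section 14.2 says that DCFBC accuracy "will be compared with multiparametric MRI using the sector-based analysis", that sensitivity and specificity are estimated for each patient, and that "differences in sensitivity and specificity between different modalities will be tested by the Wilcoxon signed-rank test". It gives no significance level, power, sector map or decision rule. Neither there nor elsewhere do the documents mention that MRI selected the men, or adjust for it.

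**The concern.** A man with prostate cancer and a negative MRI would contribute an MRI sensitivity of zero and a DCFBC sensitivity of zero or more. The entry rule removes every such man, and these are the men in whom a new tracer could add most. The signed-rank test then treats the two modalities as if neither had chosen the sample. A tracer equal to MRI could look worse, and a somewhat better one could look equal. Whole-mount histology in every man would not cure this, because the shift comes from who is enrolled and not from how truth is established.

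**Working it through.** **Inputs from the documents.** The entry rule (précis, 3.1.5.1.1, 4.2.1); 12 evaluable men in Arm 1 (4.1, 14.1); sector-based, patient-specific sensitivity with a signed-rank test (14.2).

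**Assumptions, because the documents are silent.** Sensitivity before selection is s for both modalities; each man has k cancer-bearing units detected independently of each other; the qualifying MRI finding is one of those units; the test is two-sided at 5%.

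**Step 1, the plan's own figure.** The only precision statement for Arm 1 concerns concordance: 0.70 ± 1.645 × 0.43/√12 = (0.496, 0.904), which matches the stated (0.50, 0.90). No figure is given for the MRI comparison, so there is none to reproduce.

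**Step 2, direction.** Let P be the probability that MRI shows at least one unit. MRI sensitivity is zero in MRI-negative men, so its mean among enrolled men is s/P. The DCFBC mean among enrolled men is (s − E)/P, where E is the average of DCFBC sensitivity counted only over MRI-negative men (zero for all others). The difference, MRI minus DCFBC, is therefore E/P. Given equal sensitivities before selection, it is never negative, whatever the correlation between modalities, and is zero only if DCFBC finds nothing in the men whom MRI misses.

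**Step 3, size if detection is independent.** P = 1 − (1 − s)^k, so mean MRI sensitivity among enrolled men is s/[1 − (1 − s)^k] and DCFBC stays at s. With s = 0.6:

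- k = 1: 0.6/0.6 = 1.000, shift +0.40
- k = 2: 0.6/0.84 = 0.714, shift +0.11
- k = 3: 0.6/0.936 = 0.641, shift +0.04
- k = 4: 0.6/0.9744 = 0.616, shift +0.016
- k = 6: 0.6/0.9959 = 0.602, shift +0.002

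The shift depends on s. At s = 0.5 it is +0.50, +0.17, +0.07 and +0.03 for k = 1 to 4; at s = 0.7 it is +0.30, +0.07, +0.02 and +0.006.

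**Step 4, effect on the test.** I simulated 12 men per trial, s = 0.6 for both modalities, normal approximation, zero differences dropped, 10,000 trials per setting. The table shows how often the test wrongly favours MRI (nominal 2.5%). The last two columns use a latent correlation of 0.5 between the modalities.

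| Units per man | Shift, independent | Wrongly favours MRI | Shift, correlation 0.5 | Wrongly favours MRI |
|---|---|---|---|---|
| 1 | +0.40 | 78% | +0.27 | 40% |
| 2 | +0.11 | 10% | +0.08 | 8% |
| 3 | +0.04 | 4% | +0.03 | 4% |
| 4 | +0.01 to +0.02 | 2.6% | +0.01 | 2.6% |
| 6 | under +0.01 | 2.2% | under +0.01 | 2.1% |

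**Step 5, what the cohort can estimate.** In the same simulations with 2 or more units, DCFBC detection in units that MRI showed and in units that MRI missed was the same with and without the entry rule: 60% and 60% under independence, 73% and 40% at correlation 0.5. With one unit per man, enrolled men have no MRI-missed unit.

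**The case against.** The strongest reply is that the unit of analysis is the sector. MRI can miss other cancer-bearing sectors in an enrolled man, and with four or more independent units the shift is 3 points or less at s = 0.5 to 0.7. This stands, and it is why the size must be left open. It does not remove the point: sectors covered by one lesion are likely to be seen or missed together, so the effective number of chances may be nearer the number of lesions than of sectors. The documents report neither.

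Second, section 3.1.5.1.1 asks for a suggestive MRI and for confirmed cancer, but not that the MRI lesion be the confirmed site. The précis leans that way without settling it. If false-positive MRI findings qualify men whose cancer lies elsewhere, selection on true detection is weaker. This also stands.

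Third, some related comparison is already planned. Section 4.9.3 compares PET with MR per subject and per lesion, and section 14.3 uses a PET-positive rate among sites seen on conventional imaging. The first has no stated analysis. The second is an interim measure without histology. Neither corrects the test in 14.2.

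A reader might infer that the entry rule forces MRI sensitivity to 100%, or that the test is bound to declare MRI superior. The documents do not support either: both need a single cancer-bearing unit per man or something close to it. Nor can the same be said of specificity, since false-positive MRI sectors also help a man qualify and may count against MRI.

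**Conclusion.** The point holds as to direction. MRI selects the Arm 1 men and is then compared with DCFBC in them, and no caveat is given. When the qualifying finding is true cancer, the sensitivity difference moves towards MRI relative to unselected men with localized disease. Equal sensitivities make this exact. With unequal ones it normally still holds, but not if DCFBC's advantage among MRI-positive men exceeds its sensitivity among MRI-negative men.

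The size is not determined. It runs from large (about 40 points) to negligible over a plausible range of one to six units per man, under assumed values of s, k and correlation. Severity is minor: the analysis is secondary, the arm has 12 men in a pilot, and no stated decision depends on the test.

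**What to change.** In section 14.2:

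- State that the sensitivity comparison applies to men with a positive MRI and is biased towards MRI, and that no conclusion will be drawn from it that DCFBC is inferior or equal to MRI in localized disease generally.
- Report as the main sensitivity results DCFBC detection among histology-positive sectors that MRI showed, and among histology-positive sectors that MRI missed, each with a confidence interval that accounts for clustering by patient.

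A tempting alternative is to repeat the comparison without the qualifying lesion and claim a difference only if both analyses agree in direction. I advise against it. With k units, one MRI-positive unit removed and s = 0.6, mean MRI sensitivity in the rest is [k × 0.6/P − 1]/(k − 1). That is 0.43, 0.46, 0.49 and 0.52 for k = 2, 3, 4 and 6, against 0.60 for DCFBC: a bias of −0.17 to −0.08. It cannot be computed in a man with one lesion. If MRI truly detects 70% and DCFBC 60%, the expected difference becomes −0.06 (k = 2) or −0.02 (k = 3), so a real MRI advantage would be hidden.

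The cost is a few sentences and one extra tabulation of sectors already being scored. Eligibility, scans and sample size do not change. With 12 men there will be few MRI-missed sectors, so that estimate will be imprecise.

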2.3 Rationale

We propose to further expand upon initial clinical work with ^{18}F DCFBC and evaluate its usefulness in three different categories of prostate cancer- localized, metastatic and biochemical recurrence. In the case of localized disease ^{18}F DCFBC distribution will be compared with endorectal coil multiparametric MRI at 3T. In the case of potentially recurrent or metastatic disease ^{18}F DCFBC will be compared with CT, bone scan and/or Sodium Fluoride PET/CT bone scan. This study should offer insights into how and when ^{18}F DCFBC could be used in the clinical setting to direct proper management. Moreover, by monitoring ^{18}F DCFBC uptake in metastatic disease over time, one may better understand how useful this agent may be in monitoring responses to therapy.

Amendment C Addendum:

The agent has shown some preliminary promising results. In Arm 2, we have had patients with questionable uptake only near the bladder. We have noted that bladder activity may obscure possible prostate bed recurrence, so a recent amendment was approved for urinary catheterization with possible bladder irrigation. We have only been able to scan a limited

CC Protocol Number: 14-C-0140
Abbreviated Title: DCFBC in prostate cancer
Version date: 10/27/2015
CIP #: 9622

number of patients using this technique and have been able to locate areas suspicious for recurrence in some. Additional patients will help to determine if the technique is beneficial in visualization, potentially improving detection rates for early local recurrence. In Arm 3, we have noted a mixed response in tracer uptake for hormone sensitive patients, which contradicts what other PSMA research groups are reporting. They assert that uptake is always positive in patients on anti-androgen treatment. Our findings could be due to the heterogeneous evolution of lesions to castrate resistance, but currently our numbers are small. More patients to this arm will allow better characterization of the relationship between 18F DCFBC uptake and androgen deprivation therapy.

Amendment E Addendum:

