4.3 Drug Administration

4.3.1 ^{18}F DCFBC

See Section [7.1.5](#).

4.3.2 ^{18}F NaF Injection

See section [7.2.4](#)

4.4 ^{18}F DCFBC PET/CT Imaging

All images will have personal subject identification removed and will be assigned unique subject identification.

Patients will be instructed to maintain good hydration for the 24 hours prior to the ^{18}F DCFBC PET/CT (recommended 1-2 liters of fluid, unless medically contraindicated).

CC Protocol Number: 14-C-0140
Abbreviated Title: DCFBC in prostate cancer
Version date: 10/27/2015
CIP #: 9622

Patients will report to the NCI Molecular Imaging Clinic (MIC) on the day of their ^{18}F DCFBC PET/CT imaging sessions and peripheral venous access will be obtained. The patient will be encouraged to void prior to positioning in the PET/CT scanner.

Patency of the venous access will be demonstrated with a saline flush and the patient will then receive 8 mCi of ^{18}F DCFBC as an IV bolus.

Dynamic PET/CT imaging of a single bed position (including the prostate bed) will be performed for 45-min for patients in Arm 1 and 2 then, at 60 minutes post injection of ^{18}F DCFBC. A static whole body PET/CT will be performed then repeated again at 2hrs post injection. Only a single injection of ^{18}F DCFBC is required. The initial 45 minutes dynamic regional scan will be used to determine the kinetics of ^{18}F DCFBC in the tumor as compared with normal prostate and other background.

Patients in Arm 3 will only have static whole body PET/CTs performed at 60 minutes post injection and again at 2 hrs post injection. As previous studies have suggested, increased T:B uptake is seen at 2 hours compared with 1 hour after radiotracer injection. After 5 patients are imaged in each arm, an interim analysis will be done to determine the utility of imaging at 2 hrs.

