4.9 Correlative Studies

4.9.1 Imaging Correlation

A volume of interest (VOI) will be drawn over the target lesion on the PET/CT and PET/MRI (if PET /MRI is obtained) images for each subject and Standard Uptake Values (SUVs) will

CC Protocol Number: 14-C-0140
Abbreviated Title: DCFBC in prostate cancer
Version date: 10/27/2015
CIP #: 9622

be recorded. Focal areas of abnormal uptake will be compared with any abnormalities on standard of care imaging.

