12.1.3 Imaging Data

Extracted imaging data include:

- (1) PET imaging data will include SUV for each region of interest
- (2) All image data will be stored on a secure server, with access limited to credentialed users. This will permit flexible numeric raw data extraction for quantitative analysis and creation of summary data reports.

CC Protocol Number: 14-C-0140
Abbreviated Title: DCFBC in prostate cancer
Version date: 10/27/2015
CIP #: 9622

- (3) Anonymized image data from this study will be stored in a secure database that it is administered by the Cancer Imaging Program, NCI. The data may be shared with research collaborators to improve upon current methods of image analysis. The database is password protected and access is only given to qualifying collaborators.

Imaging findings for Na¹⁸F PET/CT will be dictated into the PACS system similar to other clinical radiologic studies, but dictations for ¹⁸F DCFBC PET/CT will only reflect the radiotracer dose, injection site and a statement indicating that the scan is for research purposes only.

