14 STATISTICAL CONSIDERATIONS

14.1 Primary Analysis

This is a single site three-arm pilot study, where prostate cancer patients are enrolled into different arms according to their disease types: localized (Arm 1), recurrent (Arm 2) or metastatic (Arm 3). The primary objective of this study is to assess the ability of ^{18}F -DCFBC to identify sites of localized, recurrent and metastatic prostate cancer. To achieve this goal, ^{18}F -DCFBC PET/CT and conventional imaging will be used to identify positive suspected sites, and the proportion of positive concordance will be used to assess the performance of ^{18}F -DCFBC. In a recent study (Cho et al., 2012), 32 positive suspected sites in five prostate cancer patients with metastasis were identified by ^{18}F -DCFBC PET/CT with 21 concordant on both ^{18}F -DCFBC PET/CT and conventional imaging. At the individual level, the number of positive suspected sites ranged from 2 to 12 with the patient-specific concordance rate ranging from 0 to 100%. The overall concordance rate which was the average of individual-specific estimates across patients equaled 64% with corresponding standard deviation equal to 43%. For the new study, assume that for patients in Arm 1 and Arm 3, the mean concordance rate is 70% with 43% standard deviation as observed in Cho et al. With 12 evaluable patients in Arm 1, the 90% expected confidence interval for the mean concordance rate is (0.50, 0.90). With 20 evaluable patients in Arm 3, the 90% expected confidence interval for the mean concordance rate is (0.54, 0.86). For patients in Arm 2 (recurrent disease), it is unlikely to identify suspected lesions by conventional imaging at the baseline. These patients will be followed according to the protocol.

Amendment E Addendum:

Sensitivity of ^{18}F -DCFBC uptake in prostate cancer patients in Arm 2 is evaluated by its ability in differentiating mean values of PSA between PET-CT positive and PET-CT negative patients. To this end, the current study with sample size 35 for Arm 2 is under-powered to detect a sizeable mean difference in PSA between the two groups. Based on the preliminary data of the study, log-transformed PSA is approximately normally distributed with standard deviation equal to 1.3. Assume 1:2 allocation of PET-CT negative vs. PET-CT positive

CC Protocol Number: 14-C-0140
Abbreviated Title: DCFBC in prostate cancer
Version date: 10/27/2015
CIP #: 9622

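### Section 14.2 does not state the unit for the Arm 3 change-over-time model; if several lesions per man enter it, a patient random intercept alone generally gives a wrong standard error, in either direction.

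*Combined protocol and SAP*

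**What the plan says.** Section 14.2 says that change in uptake over time in metastatic patients will be estimated by a linear mixed model, and that a "random intercept will be used to account for the intra-patient correlation of longitudinal" uptake. It mentions no patient-specific time effect, lesion level, robust standard error or patient-level summary. It gives no significance level or decision rule for this analysis.

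Two other sections bear on the unit, and they point different ways:
- Section 4.9.1: "A volume of interest (VOI) will be drawn over the target lesion on the PET/CT and PET/MRI" images for each subject, which suggests one lesion per man.
- Section 12.1.3: "PET imaging data will include SUV for each region of interest", which allows several values per man.

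Section 4.1 gives Arm 3 two imaging visits, at baseline and 4 to 6 months later. At each visit section 4.4 has "static whole body PET/CTs performed at 60 minutes post injection and again at 2 hrs post injection". The plan does not say which of these two scans supplies the uptake value.

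**The concern.** Arm 3 men have metastatic disease, and the five-patient study cited in section 14.1 found 2 to 12 sites per man, 32 in all, or 32/5 = 6.4 on average. A lesion-level fit is therefore a realistic reading of 14.2.

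On that reading a patient random intercept leaves two gaps:
- It absorbs a man's overall level but not his own change. If a man's lesions share a change, the model still counts them as independent evidence about the mean change, and the standard error is too small.
- It has no lesion term. Stable differences between lesions, which cancel in a within-lesion change, stay in the residual, and the standard error is too large.

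Men could well differ in their change: the Précis (Design) says Arm 3 men may or may not be on therapy or about to start it. Change under androgen deprivation is a secondary objective (section 1.2), and section 2.3 gives this question as the reason for adding Arm 3 patients. The interval around that estimate is what is at stake.

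**Working it through.** **The plan's own Arm 3 figure.** The only precision figure for Arm 3 is in section 14.1. It assumes that "the mean concordance rate is 70% with 43% standard deviation". With 20 men, 0.70 ± 1.645 × 0.43/√20 = 0.70 ± 0.158 = (0.542, 0.858), which matches the stated (0.54, 0.86). That figure concerns concordance. The documents give no SD, power or interval width for change in uptake, so every variance below is an assumption.

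**Set-up.** Log SUV = patient level + lesion level + (patient-specific change at visit 2) + error, with no true mean change. From the plan: n = 20 men and 2 visits. Assumed: m = 6 lesions per man (near the 6.4 above), patient SD 0.5, residual variance ve = 0.2² = 0.04. The between-lesion variance vl and the between-man variance of change vs are varied. The patient SD cancels out of the change.

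**Formulas for equal lesion counts.**
- Residual variance the model estimates: S ≈ [2(m−1)vl + (2m−1)ve + m·vs/2]/(2m−1)
- Model variance of the mean change: 2S/(n·m)
- True variance of the mean change: (vs + 2ve/m)/n

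Setting the two variances equal gives m·vs = 2·vl when m > 1. The model's standard error is too small when m·vs > 2·vl and too large when m·vs < 2·vl.

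**One value per man (m = 1).** S = ve + vs/2, so the model variance is (2ve + vs)/n, which is the true variance. Simulation under a separate set of assumed variances gave 4.6% to 5.2% rejection at nominal 5%.

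**Six lesions, lesion SD 0.3, SD of change 0.4.**
- S = [10(0.09) + 11(0.04) + 3(0.16)]/11 = 1.82/11 = 0.1655
- Model SE = √(2 × 0.1655/120) = 0.0525
- True SE = √((0.16 + 0.08/6)/20) = 0.0931
- Ratio 0.56

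**Six lesions, lesion SD 0.6, no variation in change.**
- S = [10(0.36) + 0.44]/11 = 0.3673
- Model SE = √(2 × 0.3673/120) = 0.0782
- True SE = √((0.08/6)/20) = 0.0258
- Ratio 3.03

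**Other combinations** by the same formulas, with simulated rejection at nominal 5% (4,000 to 6,000 runs per setting):

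| Lesion SD | SD of change | Model/true SE | Rejection |
|---|---|---|---|
| 0.3 | 0.6 | 0.44 | 38% to 40% |
| 0.3 | 0.4 | 0.56 | 27% to 28% |
| 0.6 | 0.6 | 0.65 | 21% |
| 0.3 | 0.2 | 0.91 | about 8% |
| 0.6 | 0.4 | 0.89 | about 8% |
| 0.6 | 0.35 | 0.99 | about 5% |
| 0.6 | 0.3 | 1.12 | about 3% |
| 0.6 | 0 | 3.03 | about 0% |

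**The remedies.** A one-sample t-test on each man's mean lesion change stayed at about 5% in these settings, and at 3.8% to 6.4% across a wider grid of variances and lesion counts, including counts varying from 2 to 12. On that grid, adding a lesion intercept without a patient time effect did not cure the problem: rejection was 16% to 31% at six lesions when change varied between men. On one simulated data set with equal counts, the model with both extra terms gave the same standard error as the patient-level analysis, 0.0915.

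**The case against.** The strongest objection is that 14.2 never makes the lesion the unit. Its random intercept is most simply read as handling repeat visits by one man. Section 4.9.1 speaks of a single target lesion. Elsewhere the plan reduces multi-site data to one value per patient: the concordance rate in 14.1, sensitivity and specificity in 14.2, the PET-positive rate in 14.3. Section 12.1.3 describes what is stored, not what is modelled. All of this stands. On that reading the model is sound, and a patient time effect could not be separated from error.

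A reader might also infer that this analysis will declare chance changes real. The documents do not support that. Section 14.2 says that change will be estimated and attaches no test to it, so the 5% level is only a yardstick. The direction of the error depends on variances that nobody has stated, and part of the plausible range is close to nominal.

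Nor does the "mixed response in tracer uptake for hormone sensitive patients" reported in section 2.3 show that lesions in one man move together. The protocol suggests it may reflect lesions evolving differently. If change varies between lesions (SD 0.4) but not between men, the model is conservative: about 1% rejection at lesion SD 0.3 and 0% at 0.6.

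What remains is that the unit is open, the plan collects SUVs per region, and the stated model gives a reliable interval on only one of the two readings.

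**Conclusion.** The point holds as a gap in specification with a conditional consequence. If one value per man per visit is analysed, nothing is wrong. If per-region SUVs are analysed, the standard error is generally wrong, and correct only near m·vs = 2·vl. At six lesions per man and the assumed variances, the model-to-true ratio runs from about 0.56 through about 0.9 to 1.0 to about 3.0, and is lower still (0.44) if men differ more in their change.

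The claim that the analysis as planned inflates false positives goes too far: it needs the lesion as the unit, change that varies materially between men, and a test that the plan does not specify. This is a secondary analysis in a pilot study, so the change is advisable, not essential.

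**What to change.** In section 14.2, make the patient the unit. For each man, average the baseline-to-follow-up changes in log SUV over the lesions measured at both visits, using one named scan time (60 minutes or 2 hours) throughout. Report the mean of the 20 patient-level changes with a one-sample t interval (19 degrees of freedom). This is valid whether a man contributes one lesion or several.

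If lesions are to be modelled directly, specify a patient random intercept, a lesion-within-patient random intercept and a patient random time effect. The time effect is essential; a lesion intercept alone is not enough. The two approaches agree exactly only when lesion counts are equal, so name one of them in advance.

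The cost is one sentence and no new data. The interval may be wider where the present one would be falsely narrow, and narrower where lesion differences would have inflated it.
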